7. SAFETY REPORTING

7.1. Definition of adverse events

The International Conference on Harmonization (ICH) Guideline for Good Clinical Practice (GCP) E6 (R1) defines an AE as:

Any untoward medical occurrence in a patient or clinical investigation subject administered a pharmaceutical product and which does not necessarily have a causal relationship with this

Version Number: 1.8

Proprietary of MD Anderson Cancer Center Date: July 26, 2019

treatment. An AE can therefore be any unfavorable and unintended sign (including an abnormal laboratory finding), symptom, or disease temporally associated with the use of a medicinal product, whether or not considered related to the medicinal product.

An AE includes but is not limited to any clinically significant worsening of a subject's preexisting condition. An abnormal laboratory finding (including ECG finding) that requires an action or intervention by the investigator, or a finding judged by the investigator to represent a change beyond the range of normal physiologic fluctuation, should be reported as an AE.

Adverse events may be treatment emergent (i.e., occurring after initial receipt of IP) or nontreatment emergent. A nontreatment-emergent AE is any new sign or symptom, disease, or other untoward medical event that begins after written informed consent has been obtained but before the subject has received IP.

Elective treatment or surgery or preplanned treatment or surgery (that was scheduled prior to the subject being enrolled into the study) for a documented pre-existing condition, that did not worsen from baseline, is not considered an AE (serious or nonserious). An untoward medical event occurring during the prescheduled elective procedure or routinely scheduled treatment should be recorded as an AE or SAE.

The term AE is used to include both serious and non-serious AEs.

7.2. **Serious Adverse Event Reporting**

An adverse event or suspected adverse reaction is considered "serious" if, in the view of either the investigator or the MDACC IND Office, it results in any of the following outcomes:

- Death
- A life-threatening adverse drug experience any adverse experience that places the patient, in the view of the initial reporter, at immediate risk of death from the adverse experience as it occurred. It does not include an adverse experience that, had it occurred in a more severe form, might have caused death.
- Inpatient hospitalization or prolongation of existing hospitalization
- A persistent or significant incapacity or substantial disruption of the ability to conduct normal life functions.
- A congenital anomaly/birth defect.

Important medical events that may not result in death, be life-threatening, or require hospitalization may be considered a serious adverse drug experience when, based upon appropriate medical judgment, they may jeopardize the patient or subject and may require medical or surgical intervention to prevent one of the outcomes listed in this definition. Examples of such medical events include allergic bronchospasm requiring intensive treatment in an emergency room or at home, blood dyscrasias or convulsions that do not result in inpatient hospitalization, or the development of drug dependency or drug abuse (21 CFR 312.32).

Version Number: 1.8

Proprietary of MD Anderson Cancer Center Date: July 26, 2019

- 1. Important medical events as defined above, may also be considered serious adverse events. Any important medical event can and should be reported as an SAE if deemed appropriate by the Principal Investigator or the MDACC IND Office.
- 2. All events occurring during the conduct of a protocol and meeting the definition of a SAE must be reported to the IRB in accordance with the timeframes and procedures outlined in "The University of Texas M. D. Anderson Cancer Center Institutional Review Board Policy for Investigators on Reporting Serious Unanticipated Adverse Events for Drugs and Devices". Unless stated otherwise in the protocol, all SAEs, expected or unexpected, must be reported to the IND Office, regardless of attribution (within 5 working days of knowledge of the event).
- 3. All life-threatening or fatal events, that are unexpected, and related to the study drug, must have a written report submitted within 24 hours (next working day) of knowledge of the event to the Safety Project Manager in the IND Office.
- 4. Unless otherwise noted, the electronic SAE application (eSAE) will be utilized for safety reporting to the IND Office and MDACC IRB.
- 5. Serious adverse events will be captured from the time of the first protocol-specific intervention, until 90 days after the last dose of drug, unless the participant withdraws consent. Serious adverse events must be followed until clinical recovery is complete and laboratory tests have returned to baseline, progression of the event has stabilized, or there has been acceptable resolution of the event.
- 6. Additionally, any serious adverse events that occur after the 90-day time period that are related to the study treatment must be reported to the IND Office. This may include the development of a secondary malignancy.

7.3. **Assessment of Safety Parameters**

7.3.1. **Severity**

Assessment of severity is one of the responsibilities of the investigator in the evaluation of AEs and SAEs. Severity will be graded according to the NCI CTCAE v4.03. The determination of severity for all other events not listed in the CTCAE should be made by the investigator based upon medical judgment and the severity categories of Grade 1 to 5 as defined below.

- Grade 1 (mild): An event that is usually transient and may require only minimal treatment or therapeutic intervention. The event does not generally interfere with usual activities of daily living.
- Grade 2 (moderate): An event that is usually alleviated with additional specific therapeutic intervention. The event interferes with usual activities of daily living, causing discomfort but poses no significant or permanent risk of harm to the subject.
- Grade 3 (severe): An event that requires intensive therapeutic intervention. The event interrupts usual activities of daily living, or significantly affects the clinical status of the subject.

Version Number: 1.8 Date: July 26, 2019 Proprietary of MD Anderson Cancer Center

• Grade 4 (life threatening): An event, and/or its immediate sequelae, that is associated with an imminent risk of death or with physical or mental disabilities that affect or limit the ability of the subject to perform activities of daily living (eating, ambulation, toileting, etc.).

• Grade 5 (fatal): Death (loss of life) as a result of an event.

It is important to distinguish between serious criteria and severity of an AE. Severity is a measure of intensity whereas seriousness is defined by the criteria in Section 10.1. A Grade 3 AE need not necessarily be considered an SAE. For example, a Grade 3 headache that persists for several hours may not meet the regulatory definition of an SAE and would be considered a nonserious event, whereas a Grade 2 seizure resulting in a hospital admission would be considered an SAE.

7.3.2. Relationship

The investigator will provide an assessment of relationship of AEs and SAEs to the IP.

An event will be considered "not related" to use of the IP if any of the following tests are met:

- An unreasonable temporal relationship between administration of the IP and the onset of the event (e.g., the event occurred either before, or too long after, administration of the IP for it to be considered product-related),
- A causal relationship between the IP and the event is biologically implausible (e.g., death as a passenger in an automobile accident), and/or
- A clearly more likely alternative explanation for the event is present (e.g., typical adverse reaction to a concomitant drug and/or typical disease-related event).

"Related" implies that the event is considered to be "associated with the use of the drug" meaning that there is "a reasonable possibility" that the event may have been caused by the product under investigation (i.e., there are facts, evidence, or arguments to suggest possible causation).

7.4. Recording and Reporting of AEs and SAEs

The investigator (or physician designee) is responsible for verifying and providing source documentation for all AEs and assigning the attribution for all AEs for subjects enrolled.

AEs and SAEs will be recorded according to the NCI suggested criteria as listed below.

Version Number: 1.8 Date: July 26, 2019 Proprietary of MD Anderson Cancer Center

Attribution	Grade 1	Grade 2	Grade 3	Grade 4	Grade 5
			Phase I	Phase I	Phase I
Unrelated	Phase I	Phase I	Phase II	Phase II	Phase II
			1 Hase II	Phase III	Phase III
	Phase I		Phase I	Phase I	Phase I
Unlikely		Phase I	Phase II	Phase II	Phase II
			Filase II	Phase III	Phase III
Possible	Phase I Phase II	Phase I	Phase I	Phase I	Phase I
		Phase II	Phase II	Phase II	Phase II
		Phase III	Phase III	Phase III	Phase III
Probable	Phase I Phase II	Phase I	Phase I	Phase I	Phase I
		Phase II	Phase II	Phase II	Phase II
		Phase III	Phase III	Phase III	Phase III
Definitive	Phase I Phase II	Phase I	Phase I	Phase I	Phase I
		Phase II	Phase II	Phase II	Phase II
		Phase III	Phase III	Phase III	Phase III

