1.2.2. Durvalumab

Durvalumab is a human monoclonal antibody of immunoglobulin G1 (IgG1) kappa subclass that inhibits binding of programmed death ligand 1 (PD-L1). The proposed mechanism of action for durvalumab is interference of the interaction of PD-L1, expressed on cancer cells and a subset of leukocytes, with the programmed cell death protein 1 (PD-1) molecules on antigen-presenting cells and T-cells. By binding to PD-L1 on tumor cells, the mechanism of action of durvalumab includes stimulation of the patient's anti-tumor immune response.

Version Number: 1.8 Date: July 26, 2019

Proprietary of MD Anderson Cancer Center

As of the data cut-off (DCO) date (12 July 2016), an estimated 5225 patients have been exposed to 1 or more doses of durvalumab in AstraZeneca or MedImmune sponsored studies, either as monotherapy or in combination, including 2878 patients in open label trials, and 2347 patients as an estimate based on the randomization scheme in studies where the treatment arm is blinded. Additionally, more than 1700 patients have been exposed to 1 or more doses of durvalumab in externally-sponsored/investigator-initiated clinical trials (ESR/IITs). Please refer to the durvalumab IB for detailed data.

Safety data have been pooled for 4 durvalumab monotherapy studies (CD-ON-MEDI4736-1108, D4190C00002, ATLANTIC and D4193C00001 [HAWK]) for patients who received a durvalumab dose of 10 mg/kg Q2W; a total of 1645 patients are included in this pooled data set.

- Overall, AEs reported in ≥10% of patients were fatigue (31.1%), decreased appetite (22.5%), nausea (20.5%), dyspnea (17.9%), constipation (17.8%), cough (17.4%), diarrhea (16.0%), anemia (15.3%), pyrexia (15.0%), vomiting (13.4%), back pain (12.5%), pruritus (11.0%), arthralgia (10.6%) and abdominal pain (10.2%).
- AEs that were considered by the investigator as related to durvalumab in ≥5% of patients were fatigue (14.5%); nausea (7.3%); diarrhea (6.9%); hypothyroidism (6.6%); pruritus (6.4%); decreased appetite (6.0%) and rash (5.2%).

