1.6. Study Design

This study will be an open label, multi-cohort, phase II trial for the combination therapy of MEDI0457 (INO-3112) and Durvalumab (MEDI4736) in patients with HPV-16 and/or -18 related malignancies. This study will enroll 3 cohorts of patients with HPV-16/18 (+) tumors. The three cohorts are:

- 1. HPV-16/18 cervical cancer,
- 2. HPV-16/18 rare tumors (anal, penile, vulvar, vaginal), and
- 3. HIV (+) HPV-16/18 malignancies (any site).

Each cohort will have a two-stage design with predetermined stopping rules based on ORR after stage I and each cohort will function independently clinically. After each cohort completes accrual to stage I, only the two cohorts with the most responses will move on to stage 2.

Therefore, accrual to stage 2 will not start till all three cohorts have completed stage I. However, if a single cohort has a high response rate (≥4 responses out of 9 patients), the second stage of accrual may proceed prior to other cohorts completing stage I.

At the onset of the study, only patients with cervical, vulvar, or vaginal cancers will be enrolled for the first 3 slots. Once all 3 of these patients have completed the first 6 weeks of treatment, enrollment will be opened to all included cancer histotypes.

Both MEDI0457 and durvalumab treatment will continue until confirmed disease progression or unacceptable toxicity. Either treatment may be stopped by the investigator if a SAE is deemed to be related to that treatment while the other treatment continues.

The target population consists of male or female patients 18 years of age or older with recurrent or metastatic HPV 16- or 18-associated cancers with persistent or progressive disease (PD) after initial standard-of-care treatment and lacking a curative treatment option.

Eligible patients must have at least one "measurable target lesion"—according to RECIST version 1.1—that has not been previously irradiated. In addition, if the primary lesion is not large enough for a biopsy without changing radiologic findings for following response, one additional lesion

Version Number: 1.8 Date: July 26, 2019

Proprietary of MD Anderson Cancer Center

that can be safely biopsied at screening and prior to the first dose of MEDI0457 at Week 1 will be required.

All patients will receive combination treatment with MEDI0457 and durvalumab as per the **Planned Dosing Schedule (Section 4.4.1, Figure 1**, and **Table 3**).

[figure not shown]

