7.4.1. Study recording period and follow-up for AEs and SAEs

AEs and SAES will be recorded from time of first protocol-specific intervention throughout the treatment period and including the follow-up period (90 days after the last dose of Durvalumab and/or MEDI0457). For physical exams, only abnormal findings will be recorded.

During the course of the study all AEs and SAEs should be proactively followed up for each subject. Every effort should be made to obtain a resolution for all events, even if the events continue after discontinuation/study completion.

If a subject discontinues from treatment for reasons other than disease progression, and therefore continues to have tumor assessments, drug or procedure-related SAEs must be captured until the patient is considered to have confirmed PD and will have no further tumor assessments.

The investigator is responsible for following all SAEs until resolution, until the subject returns to baseline status, or until the condition has stabilized with the expectation that it will remain chronic, even if this extends beyond study participation.

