7.5. Adverse Events of Special Interest

An AESI is of scientific and medical interest specific to understanding of the IP and may require close monitoring and rapid communication by the investigator to the supporting companies. An AESI may be serious or non-serious. The rapid reporting of AESIs allows ongoing surveillance of these events in order to characterize and understand them in association with the use of this IP.

Adverse events of special interest for MEDI0457 and durvalumab include but are not limited to events with a potential inflammatory or immune-mediated mechanism and which may require more frequent monitoring and/or interventions such as steroids, immunosuppressants and/or hormone replacement therapy. These AESIs are being closely monitored in clinical studies with durvalumab monotherapy and combination therapy. An irAE is defined as an AE that is associated with drug exposure and is consistent with an immune-mediated mechanism of action and where there is no clear alternate etiology. Serologic, immunologic, and histologic (biopsy) data, as appropriate, should be used to support an irAE diagnosis. Appropriate efforts should be made to rule out neoplastic, infectious, metabolic, toxin, or other etiologic causes of the irAE. If the Investigator has any questions in regards to an AE being an irAE, the Investigator should promptly contact the Study Physician. Identified risks (listed/expected reactions) for durvalumab include: diarrhea, ALT increase, AST increase, pneumonitis, and colitis/enterocolitis.

Version Number: 1.8 Date: July 26, 2019 Proprietary of MD Anderson Cancer Center

Adverse events of special interest observed with MEDI0457 and durvalumab include:

- Colitis,
- Pneumonitis,
- ALT/AST increases/hepatitis/hepatotoxicity,
- Neuropathy/neuromuscular toxicity (i.e., events of encephalitis, peripheral motor and sensory neuropathies, Guillain-Barré, and myasthenia gravis),
- Endocrinopathy (i.e., events of hypophysitis, adrenal insufficiency, type 1 diabetes, and hyper- and hypothyroidism),
- Dermatitis,
- Nephritis,
- Pancreatitis (or laboratory tests suggestive of pancreatitis increased serum lipase, increased serum amylase),
- Infusion-related reactions, and
- Administration site reactions.

Adverse events of special interest are required to be reported within 24 hours of knowledge of the event in the database, even if the event is considered to be non-serious.

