8.3.2. Secondary

The secondary objectives will be measured by the following:

- AEs/SAEs;
- Collection of hematology, serum chemistry, urinalysis, creatine phosphokinase, thyroid function testing and pregnancy test;
- Electrocardiograms. The following parameters will be recorded for each electrocardiogram: date and time of electrocardiogram, heart rate (beats/min), PR, QRS, RR interval, QT (ms), QTcF (ms), sinus rhythm (yes/no), and overall evaluation (normal/abnormal);
- Vital signs;
- Physical examinations;
- Concomitant medications;
- OS;
- PFS as assessed by RECIST v1.1;
- ORR by RECIST v1.1;
- Immune-related RECIST; and
- Disease control rate at 24 weeks by RECIST v1.1.

Safety will be summarized by the percentage of patients with AEs, with grading(according to CTCAE v4.03) and attribution. Summary statistics will also be provided for serious AEs, hematology, urinalysis, CPK, thyroid function testing, pregnancy test, ECG, vital sign, physical examinations and concomitant medications.

Version Number: 1.8 Date: Inly 26, 2019 Proprietary of MD Anderson Cancer Center

8.3.2.1. **Objective Response Rate (ORR)**

Objective response rate will be assessed as a secondary endpoint in the As-treated Population using RECIST version 1.1. Objective response rate will be also assessed in the Response-evaluable and As-treated populations using irRECIST.

8.3.2.2. **Progression Free Survival (PFS)**

Progression free survival measures progression by growth of the primary tumor, nodal spread metastases, death from the cancer, or death from other causes. Progression free survival will be assessed by the periodic tumor assessment using imaging per the institutional guidelines at the schedules according to Table 3.

All study evaluations for disease response must be based on RECIST v1.1.

Progression free survival will be defined as the time from the date of start of IP treatment until the date of objective disease progression or death (+1 day) (by any cause) whichever occurs first. Patients who have not progressed or died at the time of the analysis will be censored at the time of the latest date of assessment from their last evaluable RECIST version 1.1 assessment. However, if the patient progresses or dies after two or more missed visits, the patient will be censored at the time of the latest evaluable RECIST version 1.1 assessment prior to two missed visits.

The PFS time will always be derived based on scan/assessment/death dates and not visit dates.

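### The protocol does not settle whether Grade 1-2 unrelated or unlikely adverse events are recorded, so the all-cause low-grade percentages planned in section 8.3.2 are undefined and, as far as the section 7.4 table governs, understated

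*Combined protocol and SAP*

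**What the plan says.** Section 1.6 sets the phase: "This study will be an open label, multi-cohort, phase II trial for the combination therapy". Section 7.4 sets the recording rule: "AEs and SAEs will be recorded according to the NCI suggested criteria as listed below". A table of five attribution levels by five grades follows. For Unrelated and Unlikely, Phase II first appears at Grade 3. For Possible, Probable and Definitive, it appears at every grade.

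The analysis is in section 8.3.2: "Safety will be summarized by the percentage of patients with AEs, with grading(according to CTCAE v4.03) and attribution". It names no restriction by grade or attribution. The denominator is clear, because section 8.2.2 uses everyone who received any investigational product.

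Other sections state recording rules without the table's filter:

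- Section 6.2 sends new or worsening illnesses to the database as AEs.
- Section 7.4 itself makes the investigator responsible for source documentation and attribution of all AEs.
- Section 7.4.1 says "AEs and SAES will be recorded from time of first protocol-specific intervention throughout the treatment period" and continues through follow-up.
- Section 7.5 says "Adverse events of special interest are required to be reported within 24 hours of knowledge of the event in the database", including non-serious events.
- Section 7.5.4 defines infusion reactions as all AEs within 48 hours of the start of infusion and wants all of them in the database.
- Section 6.5.6 requires every MEDI0457 post-treatment reaction to be recorded.
- Section 7.2 requires all SAEs to be reported whatever their attribution.

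**The concern.** A percentage of patients with AEs by grade and attribution can be read as an all-cause rate only if every AE had the same chance of entering the database. Under the 7.4 table, a Grade 1 or 2 event enters if the investigator thinks it possibly related and does not enter if the investigator thinks it unlikely. The attribution that the summary is meant to describe therefore decides whether the event exists in the data.

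This matters more here than in a randomised trial. The study has no control arm, and section 1.3.1 describes the combination as being studied for the first time in this population. Attribution rests on individual judgement, and all-cause rates are the usual check on that judgement. Section 7.3.2 allows an event to be called not related when it is typical of the disease, which could take in low-grade fatigue, nausea or loss of appetite. The safety profile is the first-listed secondary objective in section 2.2.

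**Working it through.** **Step 1. Read the table for a phase II trial.** There are 5 attribution levels × 5 grades = 25 cells. Those without Phase II are Unrelated Grade 1, Unrelated Grade 2, Unlikely Grade 1 and Unlikely Grade 2. So 4 cells are not called for and 25 − 4 = 21 are. The printed table is ragged in the extracted text, but the contrast is not an artefact, since Phase II is listed at Grade 1 in the three lower rows of the same table.

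**Step 2. Set the rules side by side for a Grade 1-2 event judged unrelated or unlikely.**

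| Section | Recorded? |
|---|---|
| 7.4 table | No |
| 6.2 | Yes, if a new or worsening illness |
| 7.4.1 | Reads as yes; no filter stated |
| 7.5.4 | Yes, if within 48 hours of infusion start |
| 6.5.6 | Yes, if a MEDI0457 post-treatment reaction |
| 7.5 | Yes, if of special interest |
| 7.2 | Yes, if serious (7.3.1 gives a Grade 2 seizure with admission as an SAE) |
| 8.3.2 | Summarised as if present |

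No section says which rule prevails.

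**Step 3. Illustrate the possible size.** The plan states no AE rate for this trial, so there is no figure to reproduce. Section 1.2.2 gives all-cause and related rates in a durvalumab pool of 1645 patients. Its counts agree with its percentages where both are given (diarrhea 263/1645 = 16.0%; Grade 3 or higher 12/1645 = 0.7%). Under the table alone, a patient is counted if the event is related at any grade, or is Grade 3 or higher at any attribution. Hence:

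- lower bound = related rate;
- upper bound = related rate + all-cause Grade 3 or higher rate.

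For fatigue, nausea and appetite, the Grade 3 or higher rate is the Grade 3 rate plus an allowance of 0.3 points for Grade 4. Section 1.2.2 puts unlisted Grade 4 events at fewer than 5 patients each, and 4/1645 = 0.24%. Grade 5 is taken as nil.

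| Event | All-cause | Lower bound | Upper bound | Share of patients lost |
|---|---|---|---|---|
| Fatigue | 31.1% | 14.5% | 14.5 + 2.9 + 0.3 = 17.7% | 13.4/31.1 to 16.6/31.1 = 43-53% |
| Nausea | 20.5% | 7.3% | 7.3 + 1.0 + 0.3 = 8.6% | 11.9/20.5 to 13.2/20.5 = 58-64% |
| Decreased appetite | 22.5% | 6.0% | 6.0 + 1.9 + 0.3 = 8.2% | 14.3/22.5 to 16.5/22.5 = 64-73% |
| Diarrhea | 16.0% | 6.9% | 6.9 + 0.7 = 7.6% | 8.4/16.0 to 9.1/16.0 = 52-57% |

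The share labelled related moves the other way. For fatigue it is 14.5/31.1 = 47% of all patients with the event, but at least 14.5/17.7 = 82% of those the table would count.

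**Step 4. Mark what does not move.** Possible, Probable and Definitive events are recorded at every grade, and all events from Grade 3 up are recorded. Section 6.7.2 defines a DLT by treatment-related toxicity, so the stopping rule in 8.1.3 is untouched. ORR does not use AE data.

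**The case against.** The strongest reply is that the table is one rule among several and nothing gives it precedence. Sections 6.2 and 7.4.1 state recording without a filter, and 7.2, 6.5.6, 7.5 and 7.5.4 bring in low-grade events whatever their attribution. A site that follows those sections may lose little. This stands, and it limits the point to an unresolved contradiction rather than a known loss of data. It does not remove the defect. Section 7.4.1 can also be read as fixing only when AEs are recorded, leaving 7.4 to say which ones, and two sites could reasonably do different things.

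A second reply is that limiting low-grade unrelated events is a deliberate choice, and that 8.3.2 merely summarises whatever is recorded. That choice is legitimate. But 8.3.2 does not state it, so a reader of the safety table would take the any-grade percentages as all-cause.

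A third reply concerns the illustration. It comes from another dataset, ignores the 48-hour capture rule, and equates the pool's related events with possible, probable or definitive here, although 7.3.2 has only a related/not-related split and does not place Unlikely. Diarrhea is a weak example, because section 7.5 lists it as an identified durvalumab risk and special-interest reporting may capture it. All of this stands. The figures show what the table alone could do and do not forecast this trial.

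**Conclusion.** The inconsistency is real and worth correcting. To the extent the 7.4 table governs, the any-grade and Grade 1-2 all-cause percentages are understated, the low-grade Unrelated and Unlikely cells are largely empty by design, and the share labelled related is inflated. In the table-alone illustration, about 43-73% of patients with four common events would leave the all-cause count. That range assumes that the pool's related events match the three upper attribution levels here, and rests on the Grade 4 and Grade 5 allowances shown above.

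A reader might go further and infer that every recorded low-grade AE will be treatment-related, or that the safety objective cannot be answered. The documents support neither. Sections 7.2 and 7.5.4 admit some low-grade unrelated events, no event is re-attributed, and related AEs of any grade, all Grade 3 or higher AEs and all SAEs remain complete. A reader might also infer that the combination will be made to look better tolerated than durvalumab alone. No comparison with the durvalumab pool is planned, so that is only a risk of later misreading.

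**What to change.** First, reconcile sections 6.2, 7.4 and 7.4.1 so that they give one answer on which AEs are recorded. If the answer is all AEs, remove or qualify the table, and 8.3.2 can stand.

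If the table stands, amend 8.3.2 as follows:

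- give all-cause percentages for Grade 3 or higher only;
- tabulate Grade 1-2 AEs as treatment-related only, and say which of the five attribution levels count as related;
- tabulate AEs of special interest, infusion reactions and administration site reactions separately, at any grade and attribution (6.5.6, 7.5 and 7.5.4 already require them in the database);
- report no all-cause any-grade percentage.

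This takes a few lines and changes neither treatment nor sample size. Keeping the table costs a narrower safety table; recording all AEs costs more low-grade data entry.
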